#### **5.2.1.2. Supply, Packaging, and Labeling**

The study drugs will be dispensed in a kit form in which paired bottles of study drugs will be dispensed to the subject, with instructions of how to self-administer the study drugs.

All Incyte investigational product labels will be in the local language and will comply with the legal requirements of each country.

#### **5.2.1.3. Storage**

The bottles of tablets should be stored at room temperature, 15°C to 30°C (59°F to 86°F).

### **5.2.2. Anagrelide (Non-Incyte Product)**

#### **5.2.2.1. Description and Administration**

Anagrelide hydrochloride or matching placebo will be provided as 0.5 mg capsules packaged in HDPE bottles.

Anagrelide or matching placebo will be self-administered as a BID oral treatment using the dose designated at the time of the screening visit for each subject.

Doses of anagrelide or matching placebo should be self-administered approximately 12 hours apart without regards to food.

Note that subjects must be instructed to withhold the morning dose of anagrelide or matching placebo until reaching the clinic for each study visit where dose administration will occur. The dose must be reduced or interrupted for declining platelet count or ANC as described in Section 5.4 and will be increased or restarted with recovery of hematologic parameters.

For patient-specific counseling information, refer to the anagrelide label ([Agrylin 2013](#)).

### **5.2.2.2. Supply, Packaging, and Labeling**

The study drugs will be dispensed in a kit form in which paired bottles of study drugs will be dispensed to the subject, with instructions of how to self-administer the study drugs.

Anagrelide or matching placebo reference therapies with marketing authorisation must be used in accordance with the storage conditions and shelf life in the manufacturer's approved label.

### **5.2.2.3. Storage**

The bottles of anagrelide or matching placebo capsules should be stored at room temperature, 15°C to 30°C (59°F to 86°F). Stability studies will be conducted on clinical batches to support the clinical study.

### **5.2.3. Instruction to Subjects for Handling Study Drug Ruxolitinib and Anagrelide and Their Matching Placebo**

The subject must be instructed in the handling of study drugs as follows:

- To store study drugs at room temperature.
- To only remove from the bottle of ruxolitinib and/or anagrelide or matching placebo the number of tablets needed at the time of administration.
- Not to remove doses in advance of the next scheduled administration.
- To make every effort to take doses of ruxolitinib and/or anagrelide or matching placebo on schedule.
- To report any missed doses at the next study visit.
- If the subject vomits after taking study drug(s), then the subject should not take another dose.
- If a dose of study drug is missed by more than 4 hours, then that dose should be skipped, and the next scheduled dose taken at the usual time.
- To keep study drug in a safe place and out of reach of children.
- To bring all used and unused study drug kits to the site at each visit.

### **5.3. Treatment Compliance**

Compliance with all study-related treatments should be emphasized to the subject by the site personnel, and appropriate steps should be taken to optimize compliance during the study. Compliance with ruxolitinib and/or anagrelide or matching placebo will be calculated by the sponsor based on the drug accountability documented by the site staff and monitored by the sponsor/designee (tablet counts). Subjects will be instructed to bring all study drugs with them to the study visits in order for site personnel to conduct tablet counts to assess study drug accountability. The drug accountability documentation will be used by the sponsor to calculate treatment compliance.

## 5.4. Treatment Modifications: Increases, Interruptions, and Adjustments

Subjects randomized to either study group will be receiving both an active drug and a placebo (dummy drug). Neither the investigator nor the subject will know which is the active drug and which is the placebo. Thus, in order to maintain the blind, when dose modification is required, both of the study drugs will be titrated together.

### 5.4.1. Dose Increases for Inadequate Efficacy

Dose increases will be permitted for inadequate efficacy. Dose increases for subjects meeting prespecified criteria for inadequate efficacy will be permitted after 2 weeks of therapy, and dose decreases for safety are allowed at any time. Doses of both study drugs will be titrated simultaneously using different dose levels as shown in [Table 2](#). Anagrelide or anagrelide placebo and ruxolitinib or ruxolitinib placebo increases are permitted per investigator discretion and taking into account the manufacturer's instructions, labeling, and subject's medical condition.

Each dose escalation must be at least 1 week apart, and subjects must meet all of the following criteria:

1. Platelet count  $\geq 150 \times 10^9/L$
2. Hemoglobin  $\geq 9$  g/dL.
3. ANC  $\geq 1500 \times 10^9/L$ .
4. One or more of the following:
  - a. Platelet count  $> 600 \times 10^9/L$ .
  - b. WBC count  $> 10 \times 10^9/L$ .
  - c. Minimal improvement, no change, or worsening of vasomotor symptoms including headache, lightheadedness, syncope, atypical chest pain, acral paresthesia, livedo reticularis, erythromelalgia, and transient visual disturbances (eg, amaurosis fugax, scintillating scotomata, ophthalmic migraine).

Additionally, it is recommended that safety hematology be performed within 14 days of a dose increase to confirm that a safe dose has not been exceeded. Doses may be increased by 5 mg BID for ruxolitinib or ruxolitinib-placebo. These are per investigator discretion and taking into account the manufacturer's instructions, labeling, and subject's medical condition. The dose of ruxolitinib or ruxolitinib-placebo will never exceed 25 mg BID.

Doses of anagrelide or anagrelide placebo may not be increased by more than 0.5 mg/day per week from the previous dose or to a dose that was not previously tolerated by the subject. The dose of anagrelide or anagrelide placebo should not exceed 2.5 mg BID (and 2.5 mg in a single dose). The maximum dose of anagrelide is 2.5 mg BID (5 mg total per day), which corresponds to a high maintenance dose used in practice.

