**Dose Titration Criteria (for Both Study Drug and Reference Therapy):**

Doses should be taken morning and evening, approximately 12 hours apart and without regards to food.

Dose escalations up to the maximum allowed dose for ruxolitinib (25 mg BID) and anagrelide (2.5 mg BID) are permitted. When modifications are made to the ruxolitinib dose, the dose of anagrelide will be modified concurrently. A dose increase of 5 mg BID up to a maximum dose of 25 mg BID is permitted after 2 weeks of treatment for ruxolitinib, and a dose increase of 0.5 mg/day per week up to a maximum dose of 2.5 mg BID is permitted for anagrelide.

Each dose escalation must be at least 1 week apart, and subjects must meet all of the following criteria:

1. Platelet count  $\geq 150 \times 10^9/L$ .
2. Hemoglobin  $\geq 9$  g/dL.
3. ANC  $\geq 1500 \times 10^9/L$
4. One or more of the following:
  - a. Platelet count  $> 600 \times 10^9/L$ .
  - b. WBC count  $> 10 \times 10^9/L$ .
  - c. Minimal improvement, no change, or worsening of vasomotor symptoms including headache, lightheadedness, syncope, atypical chest pain, acral paresthesia, livedo reticularis, erythromelalgia, and transient visual disturbances (eg, amaurosis fugax, scintillating scotomata, ophthalmic migraine).

NOTE: Dose decreases or interruptions for safety are required at any time throughout the study in accordance with Protocol requirements.

A maximum of 8 weeks of dose interruption is permitted in the study; subjects who cannot tolerate the study medications must discontinue from the study.

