#### 3.1. Subject Inclusion Criteria

A subject who meets all of the following criteria may be included in the study:

1. Men and women, aged 18 or older.
2. Subjects diagnosed with ET according to revised WHO 2016 criteria ([Appendix A](#); [Arber et al 2016](#)).
3. Subjects who are resistant to or intolerant of HU ([Appendix B](#)), that is, fulfilling at least 1 of the following criteria:
  - a. Platelet count  $> 600 \times 10^9/L$  after 3 months of at least 2 g/day of HU (2.5 g/day in subjects with a body weight over 80 kg) OR at the subject's maximally tolerated dose if that dose is  $< 2$  g/day.
  - b. Platelet count  $> 400 \times 10^9/L$  and WBC count  $< 2.5 \times 10^9/L$  or hemoglobin (Hgb)  $< 10$  g/dl at any dose of HU.
  - c. Presence of leg ulcers or other unacceptable muco-cutaneous manifestations at any dose of HU.
  - d. HU-related fever.
4. Platelet count  $\geq 650 \times 10^9/L$  at screening.
5. WBC  $\geq 11.0 \times 10^9/L$  at screening.
6. ECOG performance status 0 to 2.
7. Known status of JAKV617F mutation.

8. Willingness to avoid pregnancy or fathering children based on the following criteria ([Appendix G](#)):
  - a. Woman of nonchildbearing potential (ie, surgically sterile with a hysterectomy and/or bilateral oophorectomy OR  $\geq 12$  months of amenorrhea and at least 50 years of age).
  - b. Woman of childbearing potential who has a negative serum pregnancy test at screening and negative urinary test before the first dose on Day 1 and who agrees to take appropriate precautions to avoid pregnancy (with at least 99% certainty) from screening through safety follow-up. Permitted methods that are at least 99% effective in preventing pregnancy should be communicated to the subject and their understanding confirmed.
  - c. Man who agrees to take appropriate precautions to avoid fathering children (with at least 99% certainty) from screening through safety follow-up. Permitted methods that are at least 99% effective in preventing pregnancy should be communicated to the subject and their understanding confirmed.

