## **5.2. Study Drug**

### **5.2.1. Ruxolitinib**

#### **5.2.1.1. Description and Administration**

Ruxolitinib or matching placebo will be provided as 5 mg tablets packaged in high-density polyethylene (HDPE) bottles. Ruxolitinib or matching placebo will be self-administered as a BID oral treatment.

Doses of ruxolitinib or matching placebo should be self-administered with approximately 12 hours apart without regards to food.

Note that subjects must be instructed to withhold the morning dose of ruxolitinib or matching placebo until reaching the clinic for each study visit where dose administration will occur. The dose must be reduced or interrupted for declining platelet count, hemoglobin, or ANC as described in Section 5.4 and will be increased or restarted with recovery of hematologic parameters.

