**Table 1: Dose Interruptions for Hematologic Toxicities**

Parameter	Dose Reduction by 1 Dose Level If:	Hold If	Reinstitute Drug at 1 Dose Level Lower When Recovered to
Hematocrit (%)	< 35%	< 30%	≥ 35%
ANC ( $\times 10^9/L$ )	< $1.5 \times 10^9/L$	< $1.0 \times 10^9/L$	≥ $1.25 \times 10^9/L$
Platelet count ( $\times 10^9/L$ )	< $150 \times 10^9/L$	< $100 \times 10^9/L$	≥ $125 \times 10^9/L$

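### The hemoglobin condition for a dose increase is not aligned with the hematocrit triggers in Table 1, so one blood count can permit an increase and call for a reduction or hold

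*Protocol*

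**What the plan says.** **Increase.** Protocol Section 5.4.1 and the dose titration part of the Synopsis list conditions that must all be met before a dose increase. The red-cell condition is "Hemoglobin $\geq 9$ g/dL"; hematocrit is not mentioned. The others are a platelet count of at least 150 × 10^9/L, an ANC printed as at least 1500 × 10^9/L, and at least one sign of inadequate efficacy (platelets above 600 × 10^9/L, WBC above 10 × 10^9/L, or unimproved vasomotor symptoms). Section 5.4.1 adds that "increases are permitted per investigator discretion and taking into account the manufacturer's instructions, labeling, and subject's medical condition".

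**Decrease and hold.** The red-cell row of Table 1 reads "Hematocrit (%) < 35% < 30% ≥ 35" percent, for reduction by one level, hold, and restart one level lower. Table 1 has no hemoglobin row.

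**Strength of the decrease rule.** The Synopsis says "Dose decreases or interruptions for safety are required at any time throughout the study in accordance with Protocol requirements". Section 5.2.1.1 (ruxolitinib) says "The dose must be reduced or interrupted for declining platelet count, hemoglobin, or ANC as described in Section 5.4". Section 5.4.1, however, describes safety decreases as allowed, and Section 5.4.2.1 introduces Table 1 as guidelines.

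**Anagrelide.** Section 5.2.2.1 says "The dose must be reduced or interrupted for declining platelet count or ANC as described in Section 5.4", with no red-cell parameter. Section 5.4 says that "when dose modification is required, both of the study drugs will be titrated together".

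**The concern.** A rule for raising a dose and a rule for lowering it should not both be satisfied by the same result. For platelets they are not: an increase needs at least 150 × 10^9/L and a reduction applies below 150 × 10^9/L, so the two are exact complements. For red cells the analyte changes between the rules and the limits do not correspond. Table 7 requires hemoglobin and hematocrit from the same blood count, so a site will hold both numbers together.

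This is a safety matter. The Protocol reports anemia as the most frequent treatment-emergent event in the earlier ruxolitinib study in ET (Section 1.5.1). It also says that subjects on the higher starting doses commonly needed reductions for anemia (Section 1.4.2). Conflicting red-cell rules are therefore likely to be met in practice. Section 5.4.4 carries the same rules into open-label treatment.

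**Working it through.** The plan states no figure to reproduce. The check is whether the zones defined by the two rules overlap.

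**Inputs from the Protocol**
- Increase: hemoglobin (Hgb) ≥ 9 g/dL (Synopsis; Section 5.4.1).
- Reduce: hematocrit (Hct) < 35%. Hold: Hct < 30% (Table 1).

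**Assumption.** The documents give no conversion, so I use Hct (%) = 100 × Hgb / MCHC. The main range for MCHC is 32 to 36 g/dL; lower values are used to find where the overlap ends.

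**Where the increase limit falls on the hematocrit scale**
- MCHC 36: 100 × 9 / 36 = 25.0%
- MCHC 32: 100 × 9 / 32 = 28.1%

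Both are below the 30% hold limit.

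**Where the Table 1 limits fall on the hemoglobin scale**
- Hct 30%: 0.30 × 32 = 9.6 g/dL to 0.30 × 36 = 10.8 g/dL
- Hct 35%: 0.35 × 32 = 11.2 g/dL to 0.35 × 36 = 12.6 g/dL

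**Overlap by assumed MCHC**

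| MCHC (g/dL) | Hct at Hgb 9 | Increase condition met, Table 1 says hold | Increase condition met, Table 1 says reduce |
|---|---|---|---|
| 30 | 30.0% | none | 9.0 to < 10.5 g/dL |
| 32 | 28.1% | 9.0 to < 9.6 g/dL | 9.6 to < 11.2 g/dL |
| 33 | 27.3% | 9.0 to < 9.9 g/dL | 9.9 to < 11.55 g/dL |
| 36 | 25.0% | 9.0 to < 10.8 g/dL | 10.8 to < 12.6 g/dL |

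**When the overlap would vanish**
- Hold overlap: 0.30 × MCHC ≤ 9, so MCHC ≤ 9 / 0.30 = 30.0 g/dL.
- Reduction overlap: 0.35 × MCHC ≤ 9, so MCHC ≤ 9 / 0.35 = 25.7 g/dL.

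**Illustration.** Take hemoglobin 9.5 g/dL, hematocrit 28.5% (MCHC 9.5 / 0.285 = 33.3), platelets 700 × 10^9/L, WBC 12 × 10^9/L and an adequate ANC. Every condition in Section 5.4.1 is met, and Table 1 calls for a hold.

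**The ANC condition.** The illustration needs the ANC condition to be attainable. Table 1 reduces below 1.5 × 10^9/L. The printed 1500 × 10^9/L is a thousand times that, and read literally it would block every increase. I read it as a unit slip for 1.5 × 10^9/L.

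**The case against.** The strongest reply is that the two rules differ in force. Section 5.4.1 gives necessary conditions for an optional step, left to an investigator who must weigh the subject's condition. The Synopsis and Section 5.2.1.1 make decreases obligatory, and the Synopsis note comes directly after the increase criteria. Meeting a permission does not cancel a requirement. The Protocol also recommends hematology within 14 days of an increase and requires toxicity review at least weekly.

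Much of this stands: a careful reader may well let Table 1 prevail. But no passage says so or bars an increase while a Table 1 trigger is met, and Sections 5.4.1 and 5.4.2.1 state the duty to decrease more weakly. If Table 1 does prevail, the hemoglobin condition has no effect. A subject at hematocrit 35% or above has hemoglobin of at least 11.2 g/dL when MCHC is 32, so a limit of 9 g/dL never binds. The text is then still misleading.

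Four stronger readings are tempting, and the documents do not support them.
- *Section 5.2.2.1 is a rival rule for anagrelide.* It defers to Section 5.4, Table 1 does not distinguish the drugs, and both are titrated together. It is an incomplete summary.
- *Some subjects start treatment already below a Table 1 limit.* Inclusion criterion 3b concerns hemoglobin below 10 "g/dl at any dose of HU", as one of four alternatives. It does not describe Day 1, and no figure shows how many subjects, if any, would be affected.
- *Dose in Weeks 32–52, and so the primary response, would vary by site.* Nothing in the documents allows that to be estimated.
- *The platelet row is a model for every limit.* It separates increase from reduction, but its restart limit (at least 125 × 10^9/L) overlaps its reduction limit (below 150 × 10^9/L). The hematocrit row has no such overlap.

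**Conclusion.** The inconsistency is real. The red-cell condition for an increase and the red-cell triggers in Table 1 use different analytes and are not aligned, so one blood count can meet the first while Table 1 calls for a reduction or a hold.

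With MCHC of 32 to 36 g/dL, the conflict with a hold covers hemoglobin from 9 g/dL to about 9.6–10.8 g/dL. The conflict with a reduction continues to about 11.2–12.6 g/dL. The reduction overlap is robust, since it disappears only at an MCHC of 25.7 g/dL or less. The hold overlap depends more on the assumption and is gone at 30 g/dL.

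The conclusion rests on the assumed conversion and on reading the printed ANC condition as a unit slip. It is a safety-relevant contradiction in the dosing text. It does not show an effect on the primary endpoint, and it implies nothing about which limit is clinically right.

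**What to change.** 1. Reconcile the Synopsis titration criteria, Section 5.4.1 and the red-cell row of Table 1, so that no single blood count can qualify for an increase while meeting a Table 1 reduction or hold trigger. The choice of analyte and limits belongs to the sponsor's clinicians.
2. Correct the ANC condition in the Synopsis and Section 5.4.1 at the same time. Otherwise the increase criteria, read literally, can never be met.
3. Align the two summary sentences with the reconciled rule: Section 5.2.1.1 names hemoglobin, which Table 1 lacks, and Section 5.2.2.1 names no red-cell parameter.
4. Use one strength of wording for the duty to decrease, and state its precedence over an increase explicitly.

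No new data are needed, because hemoglobin and hematocrit are both already required in the hematology panel. The cost is a Protocol change plus a regulatory check. Appendix K records that the dose-modification criteria were revised in response to FDA comments under the special protocol assessment, so any change of limits should be checked against that agreement before it is treated as a wording correction.

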### **5.4.4. Dose Modifications for Subjects Receiving Open-Label Treatment**

The dose increase, decrease, and discontinuation rules described in Sections 5.4.1, 5.4.2, and 5.4.3 will be followed for subjects receiving open-label anagrelide or open-label ruxolitinib. Table 2 should be used to identify dose levels for the individual study medications.

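### The neutrophil criterion for dose increases is printed 1000 times too high, in the Synopsis and in Section 5.4.1

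*Protocol*

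**What the plan says.** Protocol Section 5.4.1 and the Synopsis (Dose Titration Criteria) set out the same list of conditions for raising the dose. A subject has to satisfy every item: "subjects must meet all of the following criteria". The items are a platelet floor of 150 × 10⁹/L, "Hemoglobin $\geq 9$ g/dL", "ANC $\geq 1500 \times 10^9/L", and at least one sign of inadequate efficacy (platelets above 600 × 10⁹/L, WBC above 10 × 10⁹/L, or vasomotor symptoms that have not clearly improved). The neutrophil line is identical in both places.

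Section 5.4.4 says that the dose-modification rules, including those of Section 5.4.1, "will be followed for subjects receiving open-label anagrelide or open-label ruxolitinib".

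Elsewhere the Protocol gives neutrophil limits on a quite different scale. Table 1 (Section 5.4.2.1) reduces the dose below 1.5, holds it below 1.0 and restarts at 1.25 × 10⁹/L. Section 5.4.3.1 uses 0.5 × 10⁹/L for permanent discontinuation. The white-cell entry criterion in Section 3.1 is "WBC $\geq 11.0 \times 10^9/L$ at screening".

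**The concern.** Neutrophils are part of the white-cell count, so a neutrophil floor cannot sensibly sit far above any white-cell count that the Protocol contemplates. The printed floor does. Because the list is conjunctive, one item that cannot be met disables the whole rule.

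That matters because the design depends on titration. Section 1.4.2 says that a titration approach is needed to balance benefit and risk. Everyone starts at dose level 1 in Table 2 (ruxolitinib 10 mg BID or anagrelide 1 mg BID), and three higher levels lead to 25 mg BID and 2.5 mg BID. Applied as printed, the criterion would keep every subject in both arms at or below the starting dose, in the blinded phase and in open-label treatment.

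**Working it through.** **Inputs, all from the Protocol (× 10⁹/L).** Printed neutrophil floor for an increase: 1500 (Synopsis; Section 5.4.1). Other neutrophil limits: 1.5, 1.25 and 1.0 (Table 1) and 0.5 (Section 5.4.3.1). WBC at entry: at least 11.0 (Section 3.1). Platelet floor for an increase: 150 (Section 5.4.1). Platelet reduction line: 150 (Table 1).

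**Step 1: scale against the other neutrophil limits** (printed floor ÷ limit).
- Reduction line: 1500/1.5 = 1000
- Restart line: 1500/1.25 = 1200
- Hold line: 1500/1.0 = 1500
- Discontinuation line: 1500/0.5 = 3000

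**Step 2: scale against the white-cell count.** 1500/11.0 = 136.4. The entry criterion is a minimum and not a cap, so this ratio shows scale only. The list also conflicts with itself. The platelet and symptom items can qualify a subject whose WBC is already 10 × 10⁹/L or lower, yet a neutrophil count of 1500 × 10⁹/L would require a WBC at least that high.

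**Step 3: the likely intended value.** 1500 cells/µL × 10⁶ µL/L = 1.5 × 10⁹ cells/L. A slip in the exponent leads to the same place: 1500 × 10⁶/L = 1.5 × 10⁹/L.

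**Step 4: check against the rest of the list.** The platelet floor for an increase (150) equals Table 1's platelet reduction line (150). A neutrophil floor of 1.5 would equal Table 1's neutrophil reduction line (1.5) in the same way.

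**The case against.** The strongest reply is that this is a clerical slip with little consequence. The intended value can be read from Table 1, a hematologist will take 1500 to mean 1500/µL, and the literal error blocks escalation, so nobody receives too much drug. All of that stands and limits the weight of the point. It does not remove it: this is a mandatory dosing threshold, and it should not depend on each site guessing the unit.

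The figure could also have been damaged when the PDF was read. That is possible but unlikely, since two separate sections show the same figure and neighbouring lines in the same unit read correctly.

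A reader might go further and infer that the hemoglobin floor of 9 g/dL adds no protection beyond Table 1, which reduces at hematocrit below 35% and holds below 30%. The arithmetic is tempting. At an assumed hematocrit/hemoglobin ratio of 2.8 to 3.3, hemoglobin 9.0 g/dL corresponds to hematocrit 9.0 × 2.8 = 25.2% to 9.0 × 3.3 = 29.7%, below both lines. The floor falls below the reduction line at any ratio under 35/9 = 3.89, and below the hold line under 30/9 = 3.33. The documents do not support the inference, for three reasons:
- They give no ratio.
- It needs Table 1 to be binding for anemia, and the wording is mixed. The Synopsis says "Dose decreases or interruptions for safety are required at any time throughout the study", and Section 5.2.1.1 says, for ruxolitinib, "The dose must be reduced or interrupted for declining platelet count, hemoglobin, or ANC as described in Section 5.4". But Section 5.4.2.1 presents the Table 1 values as adequate grounds under guidelines, Section 5.4.1 speaks of decreases as allowed, Section 6.3 says the dose may be adjusted, and the parallel instruction for anagrelide in Section 5.2.2.1 omits hemoglobin.
- Overlap with Table 1 is not a defect. The platelet floor has it, and so would the corrected neutrophil floor.

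Nor do Section 5.4.1 and Table 1 give contradictory orders, because "increases are permitted per investigator discretion".

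**Conclusion.** The neutrophil criterion is wrong as printed in both places, and Section 5.4.4 extends it to open-label treatment. It is too high by a factor of 1000 if the intended value is 1.5 × 10⁹/L. That the printed value is an error rests on the Protocol's own limits. That 1.5 is the right replacement is an inference from the exact unit conversion and the parallel with the platelet floor.

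The correction is worth making, and its practical effect is probably small. A reader might infer that escalation was actually prevented, or that response rates or the comparison between arms are affected. The documents support neither: they do not show how sites applied the criterion or how many subjects were candidates for an increase, and the two drugs are titrated together in both arms.

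On anemia, the documents justify at most a clarification. The increase list and Table 1 use different analytes, and Section 5.4.1 does not say how the two fit together. For example, at an assumed ratio of 3.0, hematocrit 30% is hemoglobin 30/3.0 = 10.0 g/dL. A subject with hemoglobin between 9 and 10 g/dL would then pass the increase floor while being below Table 1's hold line.

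**What to change.** Replace the neutrophil criterion with ANC ≥ 1.5 × 10⁹/L (1500/µL) in the Synopsis and in Section 5.4.1. Section 5.4.4 works by cross-reference and needs no edit. The sponsor should confirm the value, for instance against the FDA correspondence that Appendix K (Amendment 1, item 6) cites for the neutrophil and platelet criteria.

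Optionally, add one sentence to Section 5.4.1 and the Synopsis: *No dose increase is allowed while any Table 1 reduction or hold criterion is met.* This changes no Table 1 threshold. If the sponsor regards Table 1 as binding, it only states what follows; if not, it is a real clarification for the sponsor to decide.

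The cost is clerical. Section 10.5 requires sponsor and IRB/IEC approval of protocol changes. Appendix K (Amendment 2) shows that typographical corrections have already gone to sites by administrative change letter and then been folded into an amendment. No visits or tests are added, since Table 7 already requires hemoglobin, hematocrit and absolute neutrophils.
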